Official title: Whitening Efficacy of Dentifrice Containing 10% High Cleaning Silica, 0.5% Sodium Phytate and 0.5% Sodium Pyrophosphate

NCT number: NCT04238429

Document date: 05/02/2018

Study Population and Design

This clinical trial was conducted at Guanghua School of Stomatology, Sun Yat-sen University, Guangzhou, China, from May to October 2018. The study protocols were approved by the institutional review board at Guanghua School of Stomatology, Sun Yat-sen University and were in good accordance with the World Medical Association Declaration of Helsinki on ethical aspects. This eight week study used a randomized, double-blind, parallel-group design.

The participants were informed of the study purposes and told that their participation was voluntary. Informed consent forms were signed. A total of 84 adults who met with the inclusion and exclusion criteria were invited to take part in the study. The inclusion criteria were: 1) aged 18 to 70 years old; 2) good general health; 3) able to attend the clinical examinations during the eight week study period; 4) possessing more than 20 natural permanent teeth that were uncrowned or not heavily filled with restorative materials, excluding third molars; 5) having a whole-mouth mean tooth composite stain index of more than 1.5 according to the Lobene Stain Index.⁽¹⁾ Exclusion criteria were: 1) severe oral diseases or chronic diseases; 2) advanced periodontal diseases; 3) pregnant or lactating females; 4) fluorosis or tetracycline teeth ; 5) wearing orthodontic bands or partial or removable dentures; 6) taking part in other clinical trials; 7) receiving prophylaxis during the previous 3 months or tooth whitening treatment during the past 6 months; 8) allergic to the study products.

Study procedures

Eligible patients were distributed into test and control groups randomly according to computer generated random numbers externally by a dentist. This dentist kept the randomization and group allocation information. All the other study personnel did not have access to the information during the course of the study.

The patients in the test group were given toothpaste containing 10% high cleaning silica, 0.5% sodium pyrophosphate and 0.5% phytic acid, while the patients in the control group were given a negative control toothpaste containing silica base without any active ingredient. All toothpastes were identical in appearance and taste. The

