toothpaste was marked with its specific code number which represented its group allocation and this number was not decoded until the end of the study. The distribution of the toothpaste was made in a separate place to ensure that other study personnel and patients were unaware of group assignment.

The patients were asked to only use the assigned toothpaste and the same toothbrush to brush their teeth twice daily, in the morning and in the evening, for one minute. The patients were asked to maintain their other oral hygiene habits and daily eating habits. The patients were not allowed to use any other toothpastes and oral health care products, such as mouthrinse.

The patients came to the clinic to receive clinical examinations at baseline, 4 weeks and 8 weeks. The same examiner provided the clinical examinations during the course of the study. Firstly, evaluation of oral soft and hard tissues were performed. The examiner assessed soft and hard palate, oral mucosa, tongue, sublingual and mandibular areas, salivary glands and pharynx and larynx areas of each patient. Secondly, tooth stain of the anterior teeth were measured using the Lobene Stain Index. The index measures the area and intensity of extrinsic tooth stain on the facial and lingual surfaces of six lower anterior teeth and facial surfaces of six upper anterior teeth. The tooth surfaces were divided into two regions: body and gingival. For each part, the intensity and extent of extrinsic tooth stain were graded on a scale of 0-3. For stain intensity, the scale is scored as follows: 0= No stain; 1=Light stain (yellow to light brown or gray); 2=Moderate stain (medium brown); and 3=Heavy stain (dark brown to black). For stain area, the scale is scored as follows: 0= No stain detected; 1= stain covering up to 1/3 of the region; 2= Stain covering >1/3 to 2/3 of the region; and 3=Stain covering >2/3 of the region. Three variables on tooth stain were calculated for each patient. The mean Lobene stain area, intensity and composite scores were the sum of the scores on the recorded regions of tooth surfaces divided by the number of regions. The stain composite score for each region of the tooth surfaces was the stain area score multiplied by the stain intensity score.

At 4 weeks and 8 weeks, during the follow up examinations, the patients were also

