questioned by an investigator about if they had experienced any adverse events. The adverse events included discomfort while brushing, bitter or alteration in taste, any allergic reactions arising from the use of the toothpastes and any feeling of changes on oral soft tissues. Any changes in general health conditions of the patients were also monitored.

After the patient finished each examination session, the acquired data were collected by the facilitator who kept the data. The other study personnel had no way to access the patient data during the course of the study.

Statistical analysis

According to the data from a previous study on tooth stain removal, the sample size of this study was calculated. Based on a standard deviation of 0.5 for tooth stain area score, a reduction in the mean stain intensity scores of 20% between the test and control groups, a power of 80%, a significance of 0.05, and an attrition of 10%, it was estimated that 40 patients needed to be included in each group.

Chi-square test and the independent t test were conducted to compare the differences between treatment groups on sex, age and baseline Lobene stain scores. ANCOVA with baseline Lobene score as the covariate was conducted to compare the differences between groups in follow-up Lobene area, intensity and composite stain scores. For each group, paired t tests were conducted to compare the differences between baseline and each of the two follow-ups in Lobene stain scores. All statistical analyses were two sided and at a significance level of $\alpha = 0.05$.

Study Protocol and Statistical Analysis Plan

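### Do the within-group paired t tests need a stated status beside the between-group ANCOVA?

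*Combined protocol and SAP*

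**What the plan says.** The Statistical analysis section sets out the follow-up analyses in two consecutive sentences. For the comparison of arms: "ANCOVA with baseline Lobene score as the covariate was conducted to compare the differences between groups" in the area, intensity and composite scores at follow-up. For change over time: "For each group, paired t tests were conducted to compare the differences between baseline and each of the two follow-ups in Lobene stain scores". One rule then covers everything: "All statistical analyses were two sided and at a significance level of" 0.05. No sentence ranks the tests or says which of them carries the efficacy conclusion.

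Two other statements bear on the point. The sample size in the same section rests on "a reduction in the mean stain intensity scores of 20% between the test and control groups". Under Study procedures, the comparator is "a negative control toothpaste containing silica base without any active ingredient", and for both arms "The patients were not allowed to use any other toothpastes and oral health care products, such as mouthrinse".

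**The concern.** A paired test asks whether stain changed in one arm. The trial asks whether the test paste differs from the control paste. Stain may fall in both arms for reasons unrelated to the test ingredients: the control paste is itself silica-based, brushing is set at twice a day for one minute, and other oral care products are banned. A paired test counts that shared fall; the randomised comparison removes it.

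The paired tests outnumber the between-group comparisons two to one and share their significance level. A report could therefore show a significant reduction from baseline with the test paste, and none with the control paste, and present that contrast as proof of efficacy. If that were the plan, the chance of a false claim could be well above the nominal level.

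**Working it through.** **Count of tests.** Study procedures defines three scores (area, intensity, composite) and two follow-up visits (4 and 8 weeks). There are two arms.
- ANCOVA comparisons: 3 × 2 = 6.
- Paired tests: 3 × 2 × 2 = 12, taking the Lobene scores in that sentence to mean all three. Six are in the test arm and six in the control arm.

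**Inputs for size.** From the plan: SD 0.5 (area score), 40 per arm, 10% attrition, so 40 × 0.9 = 36 evaluable per arm. Assumed, because the documents do not give it: a correlation r between baseline and follow-up of 0.5, 0.7 or 0.8. The plan states no error rate or detectable change for the paired tests, so there is no figure of its own to reproduce here.

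**Smallest significant change, each test on the same inputs.**
- Paired test: SD of change = 0.5 × √(2(1 − r)); threshold = t(0.975, 35) × SD / √36, with t = 2.030.
- ANCOVA: residual SD = 0.5 × √(1 − r²); threshold = t(0.975, 69) × SD × √(2/36), with t = 1.995.

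| r | SD of change | Paired threshold | Residual SD | ANCOVA threshold | Ratio |
|---|---|---|---|---|---|
| 0.5 | 0.500 | 0.169 | 0.433 | 0.204 | 83% |
| 0.7 | 0.387 | 0.131 | 0.357 | 0.168 | 78% |
| 0.8 | 0.316 | 0.107 | 0.300 | 0.141 | 76% |

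The paired test reaches significance on a somewhat smaller observed change, but not a drastically smaller one. Setting 0.169, 0.131 and 0.107 against the 0.335 that an unadjusted two-sample t test detects with 80% power would give 51%, 39% and 32%. That is not like for like: it compares an observed threshold with a true difference, and it credits the correlation to the paired test but not to the ANCOVA.

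**The misreading, with identical pastes.** Let p be the probability that one arm shows a significant fall (noncentral t, 35 degrees of freedom). The arms are independent, so a significant fall in the test arm only has probability p(1 − p). For example, with r = 0.5 and a shared fall of 0.1, 0.214 × 0.786 = 0.168. For one score at one visit:

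| Shared true fall (assumed) | r = 0.5 | r = 0.7 | r = 0.8 |
|---|---|---|---|
| 0 | 2.4% | 2.4% | 2.4% |
| 0.1 | 16.8% | 21.9% | 24.8% |
| 0.2 | 22.9% | 12.5% | 4.0% |
| 0.3 | 5.8% | 0.5% | 0.02% |

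In a simulation with shared falls of this kind (20,000 trials per scenario, 36 per arm), the ANCOVA wrongly favoured the test paste in 2.3% to 2.7% of trials, as it should.

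**What the plan's wording supports.** The ANCOVA sentence gives its purpose as comparing the groups. The paired-test sentence gives its own as comparing visits inside each group. The design is randomised with a negative control, and the sizing sentence refers to a difference between arms. All of this points to the ANCOVA as the efficacy analysis.

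**The case for a change.** The best argument for a change is that a plan should not leave the status of most of its follow-up tests to inference. Two-thirds of the follow-up p values (12 of 18) do not compare the pastes, all share one alpha, and one added sentence would remove the ambiguity at almost no cost while keeping every test. The table shows that the misreading could produce a false claim in up to about a quarter of trials on a single score and visit.

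Part of this stands. The status is indeed unstated, a within-arm fall is not efficacy evidence, and a label would do no harm. But 12 of 18 overstates the exposure. A significant fall in the control arm cannot be taken for efficacy of the test paste; it would reveal the shared change. The quarter is the top of a range that falls to almost nothing for a shared fall of 0.3, and it applies only if the planned ANCOVA is disregarded.

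A stronger version of the sentence would also name the score and visit that decide efficacy. The plan does not name them, but that concerns the primary endpoint and multiplicity among the six ANCOVA comparisons. It is a separate question, which labelling the paired tests would not settle.

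**Conclusion.** No change follows. The observation is accurate: 12 paired tests at two-sided 0.05 have no stated status. It is, however, a gap in wording that an analyst fills sensibly from the design, the sizing statement and the purpose given for each test. The between-group ANCOVA is planned and unaffected, and a label would change no estimate, error rate or sample size. At most the six test-arm paired p values could be misread.

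The range of about 0.02% to 25% rests on assumed correlations of 0.5 to 0.8, assumed shared falls of 0 to 0.3, the plan's area-score SD of 0.5 and 36 evaluable patients per arm. It quantifies a misuse that the plan does not propose. The conclusion would differ if a report based its efficacy claim on the within-arm tests; nothing in the plan says that it will.

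### Three stain scores with follow-up at weeks 4 and 8 are each tested at 0.05 with no primary, testing order, adjustment or success rule, so a whitening claim resting on any one result carries more than 5% error

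*Combined protocol and SAP*

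**What the plan says.** Under Study procedures: "The patients came to the clinic to receive clinical examinations at baseline, 4 weeks and 8 weeks". The stain outcomes are introduced as equals: "Three variables on tooth stain were calculated for each patient". They are mean area, mean intensity and a mean composite, and the composite is built from the other two: "The stain composite score for each region of the tooth surfaces was the stain area score multiplied by the stain intensity score".

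Under Statistical analysis, ANCOVA adjusted for baseline is used to "compare the differences between groups in follow-up Lobene area, intensity and composite stain scores". That sentence does not say which follow-up visit. The next sentence, on within-group paired t tests, refers to "each of the two follow-ups in Lobene stain scores". The section ends: "All statistical analyses were two sided and at a significance level of" 0.05.

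The sample-size sentence reads "Based on a standard deviation of 0.5 for tooth stain area score, a reduction in the mean stain intensity scores of 20" per cent. It takes its SD from one score and its effect from another, and mentions no visit.

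No section names a primary outcome or time point, a hierarchy, an adjustment, or what pattern of results would count as success.

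**The concern.** The title poses a single question, whether the test paste whitens teeth, but the plan does not say which test answers it. Nor does it say what is concluded if area is significant and intensity is not, or if week 4 and week 8 disagree. As written, a significant result on any score at any analysed visit could be put forward as the efficacy finding, each at an uncorrected 0.05.

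Under that use, 5% is the error rate of each test, not of the conclusion. For the same reason, the 80% power in the sample-size sentence cannot be attached to any particular test.

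**Working it through.** **Inputs from the documents.** Three scores; two follow-up visits; two-sided 0.05 for every test; 40 per group with 10% attrition, so 40 × 0.9 = 36 completers per group; 80% power. The documents state no overall error rate, so there is no figure of the plan's own to reproduce here. The 40 per group cannot be rebuilt either, because the control mean behind the 20% reduction is not given. It is used below only to price the fix.

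**Number of tests.** 3 scores × 2 visits = 6 between-group ANCOVAs. Baseline comparisons and within-group paired t tests are not counted, since they do not compare the pastes on efficacy.

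**Reference points for an any-one rule.**
- Six independent tests: 1 − 0.95^6 = 0.265 in either direction; 1 − 0.975^6 = 0.141 favouring the test paste.
- Perfectly correlated tests: 0.05 and 0.025.

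The truth lies between these if the scores are positively related, as the definition of the composite makes likely.

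**Allowing for the composite.** The composite is area times intensity in each region, so it should be tied to each part more closely than the parts are tied to each other. I approximated it as the standardised sum of the two. If area and intensity have correlation r, the composite then has correlation √((1 + r)/2) with each: 0.87 at r = 0.5 and 0.99 at r = 0.95. Correlated normal test statistics were simulated under no treatment effect (2,000,000 draws per setting, critical value 1.96). The correlations are those between the baseline-adjusted test statistics, and they are assumptions.

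| Area–intensity / between-visit correlation | Any of six, either direction | Any of six, favouring test paste |
|---|---|---|
| 0.5 / 0.5 | 17.1% | 8.6% |
| 0.7 / 0.7 | 14.0% | 7.0% |
| 0.9 / 0.9 | 9.8% | 4.9% |
| 0.95 / 0.9 | 9.0% | 4.5% |

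If the ANCOVA were confined to one visit (three tests), the same model gives 9.7% at r = 0.5 and 6.5% at r = 0.95 in either direction.

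**All-must-succeed rule.** A false claim requires every true-null test to be significant by chance, so the error cannot exceed that of a single test, 0.05. It reaches 0.05 only when all effects but one are real and large.

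**Cost of adjustment.** Holm's first step for six tests is 0.05/6 = 0.0083. With 36 per group, a two-sample t test has 80% power at 0.05 for a standardised difference of 0.67; at 0.0083 its power for that difference is 55%.

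**The case against.** The strongest reply is that the documents never say any one result suffices. If the sponsor meant to claim efficacy only when all scores agree, there is no inflation. That is correct, and it is why the percentages are conditional. It does not supply the missing rule.

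A second reply is that the scores overlap so heavily that they amount to one test. Overlap reduces the excess but removes it only at perfect correlation. In the model above, the any-one risk is still 9.0% at 0.95/0.9.

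Three stronger readings are tempting and should be resisted.

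- **A larger figure.** A reader might apply one common correlation of 0.5 to all pairs of scores and reach about 22% for six tests, or quote the independence figure of 26.5% as the trial's error rate. The first treats the composite as no closer to its own components than they are to each other, which sits badly with its definition. The second treats the scores as unrelated. Neither is the trial's error rate.
- **An endpoint chosen after the fact.** The analysis section is in the past tense, so a reader might infer that it was written with results in hand. The document date, 05/02/2018, points the other way: read as 5 February or 2 May, it falls before or around the start of a trial run between May and October 2018. The text also says of the toothpaste code that "this number was not decoded until the end of the study". The documents do not settle the timing, and nothing shows selection.
- **An implied primary.** The sample-size sentence, or the composite threshold for entry, might be read as naming one. The former mixes two scores and gives no visit; the latter is an eligibility criterion.

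One textual doubt stands: the ANCOVA sentence does not name its visits. Since Study procedures places follow-up examinations at both weeks 4 and 8, and nothing limits the comparison to one, six is the natural count.

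**Conclusion.** The concern holds. The omission is a matter of text and depends on no assumed correlation: the plan has no primary score or visit, order, adjustment or success rule for its between-group tests.

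The consequence is conditional. If any one of six results can carry the whitening claim, the error rate is above 5%. The illustrative size is about 9–17% in either direction and about 4.5–9% favouring the test paste, against 2.5%; the latter is the more relevant comparison for a claim of benefit. The range rests on the assumed correlations and on treating the composite as a sum. It is not a bound, and the documents do not allow a definite figure. The mismatch between the area SD and the intensity effect in the sample-size sentence is a separate issue; it matters here only because it means that sentence cannot identify the primary.

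**What to change.** First, state whether the analysis text was fixed before the group codes were broken, since the document date and the past-tense wording point in opposite directions. Then:

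- **If it was fixed before unblinding and results are still unseen:** name one score at one visit as the primary ANCOVA at two-sided 0.05. The choice is the sponsor's. Either test the other five in a stated fixed order, stopping at the first non-significant result, or label them secondary with no confirmatory claim.
- **If results have been seen:** do not choose a primary, or the number of tests, afterwards. Report all six between-group tests with Holm-adjusted p-values, or label all six non-confirmatory.

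Neither route needs extra visits or measurements; the work is SAP wording or recalculated p-values. The price is in what can be claimed. Under a fixed order, later scores cannot be claimed once one fails. Holm's first step of 0.0083 takes a test with 80% power at 0.05 down to about 55%. Holm is also conservative with correlated scores: in the model above, the chance that the smallest of six null p-values falls below 0.0083 is 1.7–3.4%.
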